## 4.7. Randomization, blinding and code breaking

This is a Quadruple-blind study and either the Participant, Care Provider, Investigator, Outcomes Assessor will be aware of treatment assignments prior to the final database locks at the conclusion of the study.

Computer-generated random numbers will be used for randomization. Both caffeine tablets and placebo tablets will be packed into identical white HDPE (High Density Polyethylene) plastic bottles numbered from 1 to 110 by a pharmacist or an independent third party. according to the list of computer-generated random numbers. After packing each bottle according to this list with either Caffeine tablets or placebo tablets, the list will be placed in a sealed envelope until completion of the trial. The label of each bottle will indicate only the patient's random number and the direction

28.02.2025

for taking the tablets. This number will be clearly noted on each patient's CRF forms and tablets would be provided hence.

The caffeine and placebo tablets will be manufactured in identical shape and size and will be film coated to give the same appearance.

Bottles containing 60 caffeine tablets will be issued on day of allocation and will contain medication required for 30 days. The packed and sealed bottles will be stored at the University of Kelaniya, Faculty of Medicine, under recommended storage conditions specified by the manufacturer and kept under lock and key and released in small batches to be given to patients. Therefore, all investigators and patients will be blinded.

The codes can be accessed any time and in the event of a Serious Adverse Effect(SAE) or a Serious Adverse Reaction(SAR) the code of that patient will be broken. All eligible participants are randomly assigned to the two groups according to patient recruitment order.

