#### 7.1. The severity of adverse events is characterized as follows

Mild: Any symptom of which the subject is aware, but which is easily tolerated.

**Moderate:** Any symptom which is discomforting enough to cause interference with a volunteer's usual activity.

**Severe:** Any symptom which causes a volunteer's inability to perform usual activity For all AEs, information will be obtained to determine causality.

The causal relationship between the investigational caffeine product and the AE will be characterized according to the following:

**Not related** – there is not a reasonable possibility that the study drug caused the AE.

**Unlikely** – suggests that only a remote connection exists between the study drug and the event. Other conditions, including concurrent illness, progression or expression of the disease state or reaction to concomitant medication, appear to explain the AE.

**Possible** – suggests that the association of the AE with the study drug is unknown, however the event is not reasonably supported by other conditions.

**Probable** – suggests that a temporal sequence of the AE with drug administration exists and, in the Investigator's clinical judgment, it is likely that a causal relationship exists between the drug administration and the AE, and other conditions (concurrent illness, progression or expression of the disease state, or concomitant medication reactions) do not appear to explain the AE.

Events where a causal relationship is classified as probable or possible will be regarded as related.

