#### 7.2. Outcome

The outcome of the adverse event will be classified according to the following definitions:

**Recovered / resolved:** the event has resolved (no further symptoms are present, and no treatment is being received by the subject).

Recovered / resolved with sequelae: the event has resolved but lingering effects may be present.

**Fatal** / **life threatening:** the subject died as a result of the event. This code should only be used for the event that caused the death, not any event that was present at the time of the subject's death.

28.02.2025

**Unknown:** will be used in the event that the subject is lost to follow-up and no reliable data can be obtained.

All observed AEs will be reported as described in the following sections.

Medically qualified investigators will obtain appropriate information to determine the outcome of the AE and to assess whether it meets the criteria for classification as a Suspected Unexpected Serious Adverse Reaction (SUSAR) requiring immediate notification.

The codes can be accessed all 24hrs and in the event of a SAE when the code of that patient will be broken.

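### The code is broken for every serious adverse event, related or not, and nothing requires the causality grade to be recorded first

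*Protocol*

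**What the plan says.** Protocol section 4.7 sets the blind. Its opening sentence reads "either the Participant, Care Provider, Investigator, Outcomes Assessor will be aware of treatment assignments prior to the final database locks". The printed word *either* must be a slip for *neither*, because the design is called quadruple-blind and the same section ends its account of packing and storage with "Therefore, all investigators and patients will be blinded". On the randomization list it says "the list will be placed in a sealed envelope until completion of the trial".

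The same section then says that the codes are accessible at any time and that "in the event of a Serious Adverse Effect(SAE) or a Serious Adverse Reaction(SAR) the code of that patient will be broken". Section 7.2 repeats the rule, with round-the-clock access, for SAEs alone: "in the event of a SAE when the code of that patient will be broken".

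On causality, section 7.1 has every adverse event graded as not related, unlikely, possible or probable, and names the Investigator's judgment in the last category. It adds: "Events where a causal relationship is classified as probable or possible will be regarded as related". On SUSAR status, section 7.2 says: "Medically qualified investigators will obtain appropriate information to determine the outcome of the AE and to assess whether it meets the criteria". The safety part of section 4.8 lists relatedness for each event. Criterion 4 of the stopping criteria in section 7.7 depends on an event being assessed as possibly or probably drug related.

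**The concern.** Being able to open the code quickly is a proper safety provision and is not criticised here. The fault lies in the trigger. As written, the occurrence of an SAE is enough, and the break is mandatory. An admission with no plausible link to the tablets would open the code just as a suspected reaction would.

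Two things are at stake. First, participants are unblinded without need in a trial that presents itself as quadruple-blind. Second, the relatedness grade of the most serious events loses its protection. The line between unlikely and possible decides whether an event counts as related, and it is a matter of judgment. Section 6.1 names known effects of caffeine, such as palpitations and raised blood pressure. An assessor who knows the assignment could be drawn towards possible for a caffeine patient and towards unlikely for a placebo patient. The grade is reported, and it also enters a rule for stopping dosing.

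**Working it through.** **Passages side by side**

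| Question | Protocol text | What follows |
|---|---|---|
| Who is blinded, and until when? | 4.7: participant, care provider, investigator and outcomes assessor, until final database lock | No exception is attached to the statement |
| When is the list opened? | 4.7: sealed until the trial is complete | No exception is attached here either |
| What breaks the code? | 4.7: an SAE or an SAR; 7.2: an SAE | Mandatory; no condition of relatedness or clinical need |
| Who authorises the break, who holds the list, who receives the code? | 4.7 says who packs the bottles; none of these three is named | Left open |
| Who grades causality and SUSAR status? | 7.1 and 7.2: the investigators | These are blinded staff |
| Is the grade recorded before the code is opened? | Not stated in 4.7, 7.1 or 7.2 | Left open |

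**Does SAE here mean only related events?** Section 4.7 expands the abbreviation as an adverse *effect*, which might suggest so. Three points speak against it. Section 4.7 lists SARs separately, which would be redundant if SAEs were already reactions. Section 7.2 uses SAE alone. Section 7.3 takes the definition of a serious adverse event from GCP, and section 7.1 allows any adverse event to be graded not related. The rule therefore covers unrelated events.

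**How many participants?** The protocol gives no expected SAE rate, so there is no planned figure to reproduce. The only input taken from it is the sample size in section 4.4: 2 × 55 = 110. The per-patient SAE risk *p* over the six months is an assumption. Expected number unblinded = 110 × *p*. With patients independent, the chance of at least one break = 1 − (1 − *p*)^110.

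| Assumed *p* | 110 × *p* | Chance of at least one break |
|---|---|---|
| 1% | 1.1 | 66.9% |
| 2% | 2.2 | 89.2% |
| 5% | 5.5 | 99.6% |
| 10% | 11.0 | above 99.9% |

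The number is small throughout this range, but the rule would more likely than not be used at least once even at the lowest rate.

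**The case against.** The strongest reply is that section 4.7 has code breaking in its title, states a general blind, and then gives an exception for the individual patient. A specific exception to a general rule is ordinary drafting. This stands in part: a reader might infer that the two statements flatly contradict each other, and that is more than the text supports. The exception is drawn too widely, and neither the blinding statement nor the sealed-list statement is worded to allow for it.

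Second, a reader might infer that all SAE causality will be judged unblinded. The documents do not say so. They do not state who receives the code, and section 7.2 mentions the SUSAR assessment before the code break. That order of sentences is not a requirement, however, and nothing else protects the assessor's blind. Unblinded grading is permitted, not prescribed.

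Third, a reader might infer a biased between-arm test of related events. Section 4.8 plans only descriptive safety summaries and a listing, so no such test is specified. The possible harm is to the recorded grades themselves.

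Fourth, a reader might infer that the primary comparison is compromised. LSM and CAP are Fibroscan readings and FIB-4 is calculated. Entry is limited to ages 18 to 65 and excludes symptomatic heart disease and caffeine sensitivity, so SAEs may be few. Some affected patients may also stop treatment. This objection largely stands.

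Finally, the DSMB in section 7.8, which includes a clinical pharmacologist and a statistician, reviews SAE reports. That is a real second look, but it does not restore a grade made with the assignment known.

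**Conclusion.** The point holds in a limited form and should be corrected. Sections 4.7 and 7.2 prescribe a code break for every SAE, without regard to relatedness or need. This unblinds more patients than the stated blind and the sealed list can accommodate, and it leaves open that relatedness and SUSAR status are judged with the assignment known.

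The mandatory trigger and the missing conditions rest on the text alone. Reading *either* as *neither* is a correction, but the rest of section 4.7 requires it. The size, about 1 to 11 of 110 participants, rests wholly on an assumed SAE risk of 1% to 10%. Unblinded grading is a possibility that the wording leaves open, and the direction of any bias in the grades is plausible but not shown. The sample size and the type I error are unaffected, and any effect on the primary endpoints is probably small. This is a matter for code-break wording in the protocol, so an analysis plan that is not at hand would not settle it.

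**What to change.** Amend sections 4.7 and 7.2 together:

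- State that an SAE does not by itself break the code. Keep the 24-hour access already described for cases where the assignment is needed for the patient's care.
- Require the investigator's causality grade to be recorded before any code is opened.
- Name the holder of the list and say who may receive a code. Where SUSAR reporting needs the assignment, send it to the ERC and DSMB without informing site staff.
- Word the database-lock and sealed-list statements so that they allow for this defined exception.
- Log each break with date, reason and recipient.
- Correct *either* to *neither* in the opening sentence of section 4.7.

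The cost is a wording amendment, a short log and one extra step when an SAE or SUSAR is reported. A custodian must also be named: section 4.7 says that a pharmacist or independent third party packs the bottles, but not who keeps the envelope. Sample size and visit schedule do not change.

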## 4.8. Data analysis:

Data will be analyzed using SPSS software version 21. Baseline patient characteristics will be described using descriptive statistics. Continuous variables will be expressed using mean and standard deviation or median with range depending on the distribution of data. Categorical variables will be expressed using frequency and percentage. Primary analysis will be done using a modified intention to treat (mITT) analysis where only subjects with at least one follows up assessment done will be included in the analysis.

Mean change in CAP score and LSM from baseline to 6 months will be compared between the 2 groups (Caffeine tablets vs placebo) using Independent T test or Mann Whitney U test depending on the distribution of data. For the secondary endpoints continuous variables will be compared using Independent T test or Mann Whitney U test and categorical variables will be compared using Chi square test. Repeated measures ANOVA will be used for analysis of change in variables from baseline till end of study. P value less than 0.05 will be considered statistically significant.

Safety outcomes will be described using descriptive statistics. For patients who were lost to follow up, the last available value will be used for analysis.

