## 2.2. Objectives:

#### **Primary Objective:**

To assess the effect of coffee (caffeine) supplementation on hepatic steatosis and fibrosis
in NAFLD patients measured by CAP score using Fibro scan and Hepatic fibrosis
measured by TE using Fibro scan and FIB-4 scores

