#### Calculation,

Adjusting for Dropout (20%)

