#### 5.5. Follow up assessment

The recruited patients will be advised to come for monthly assessments and will be asked to attend the nearest hospital, if they develop any complications and inform the study team of such incidence.

The degree of adherence to prescribed lifestyle changes and diet will be recorded at the baseline and monthly follow-up visits. Physical activity and alcohol consumption will also be monitored at the baseline and monthly follow-up visits.

Anthropometric measurements, physical examination and vital sign measurements (BP, HR, RR etc..) will be monitored at the baseline and each monthly visit. Details on concomitant medications will be recorded in monthly visits.

Liver profile, Lipid profile, Full blood count, Serum creatinine, fasting blood glucose, HbA1c, serum insulin, serum electrolytes and urine analysis and serum insulin will be investigated at the baseline, at 3 months and 6 months.

Fibro scan will be done at the baseline and after 6 months at the completion of the study.

The details of items which will be measured on every visit are described in Table 2.

Table 2: Summary of follow up

	Enrolment	Allocation 1	Subsequent visits							
TIME POINT		0	1 st	2 nd	3 rd	4 th	5 th	6 th		
			mont	mont	month	mont	month	mont		
			h	h		h		h		
ENROLMENT										
Eligibility screen	×									
Informed consent	×									
Allocation		×								
INTERVENTIO										
NS										
caffeine or		×	×	×	×	×	×			
placebo										
ASSESSMENTS										
Medical history	×	×	×	×	×	×	×	×		
taking										
AUDIT	×	×	×	×	×	×	×	×		
FFQ and IPAQ	×	×	×	×	×	×	×	×		

Height, weight			×	×	×	×	×	×
and waist								
circumference								
Blood pressure	×	×	×	×	×	×	×	×
Physical examination 	×	×	×	×	×	×	×	×
USS scan	×							
Fibro scan		×						×
FBG	×	×			×			×
Fasting serum insulin		×			×			×
HCG only female	×							
Serum HbA1c		×			×			×
Lipid profile	×	×			×			×
Liver enzymes	×	×			×			×
Total bilirubin	×				×			×
Serum creatinine		×			×			×
Serum electrolytes		×			×			×

FBC	×		×		×
UFR	×		×		×

28.02.2025

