#### **Risks**

There is a risk of participants experiencing side effects of caffeine such as palpitations, high blood pressure, gastrointestinal discomfort, insomnia and anxiety

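### The primary analysis set leaves out randomised participants with no follow-up assessment, so losses before the month-1 visit, which may differ by arm, fall outside the randomised comparison

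*Protocol*

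**What the plan says.** Section 4.8 (Data analysis) states that the primary analysis is a "modified intention to treat (mITT) analysis where only subjects with at least one follows up assessment done will be included in the analysis". The same section adds: "For patients who were lost to follow up, the last available value will be used for analysis". It names no analysis of all randomised participants.

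Other parts of the protocol bear on this rule:

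- **Objective (2.2).** "To assess the effect of coffee (caffeine) supplementation on hepatic steatosis and fibrosis" in NAFLD patients. Neither the objective nor the hypotheses in 2.1 are limited to people who return for a visit.
- **Visits (5.5).** "The recruited patients will be advised to come for monthly assessments". The first scheduled visit after allocation is therefore at month 1.
- **Outcome measurement (5.5).** "Fibro scan will be done at the baseline and after 6 months at the completion of the study". Section 4.6 and Table 2 agree. The synopsis, however, lists fibroscan findings under data collected at 3 and 6 months.
- **Tolerability.** The Risks paragraph of 6.1 names "side effects of caffeine such as palpitations, high blood pressure, gastrointestinal discomfort, insomnia and anxiety". Section 5 describes the placebo as inert starch. Section 7.7 allows a participant to be terminated or withdrawn for adverse events or inability to tolerate the tablets.
- **Entry (4.3.2).** People with known sensitivity to caffeine, symptomatic ischaemic heart disease or arrhythmia are excluded.

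**The concern.** Randomisation protects the comparison when everyone randomised is compared. Here, membership of the primary set depends on something that happens after randomisation: having one follow-up assessment. One arm takes a substance with recognised early side effects and the other takes starch. Loss in the first month could therefore be related to treatment, and the two analysed groups could stop being comparable. The estimate would also answer a narrower question than the objective asks, because it would cover only participants who reached a first follow-up.

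The usual defence of a modified set is that it keeps the participants who have outcome data. That does not apply here. On the section 5.5 schedule, the month-1 visit yields no CAP or LSM. Someone who leaves in week 3, and someone who attends month 1 and leaves in week 5, both have a baseline scan only. The first is deleted. The second is kept with baseline carried forward, which counts as zero change.

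**Working it through.** **Inputs from the protocol (4.4).** Mean difference 3, SD 5, two-sided alpha 0.05, power 80%, dropout 20%, 55 per group. The endpoint and units of the 3 and the 5 are not named, so results below are in those unnamed units.

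**The plan's own figure.** n per group = 2 × 5² × (1.96 + 0.84)² / 3² = 43.6, rounded to 44, and 44 / 0.8 = 55. The stated 55 per group (110 in total) is reproduced with the standard two-group formula. A 20% dropout is 11 participants per group. The protocol does not split it by arm or by time.

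**Assumptions not in the protocol.** Early leavers gain no benefit from caffeine, the placebo mean does not change, and early loss is from the caffeine arm only. Let e be the number of caffeine participants who leave before month 1.

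**Step 1: early loss only.** The effect in all randomised is 3 × (1 − e/55). The mITT set shows 3.0. The relative excess is 55/(55 − e) − 1.

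| e | all randomised | mITT | excess |
|---|---|---|---|
| 3 | 2.84 | 3.0 | 5.8% |
| 5 | 2.73 | 3.0 | 10.0% |
| 11 | 2.40 | 3.0 | 25.0% |

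**Step 2: early and later dropout together.** Take 11 caffeine dropouts, 5 of them early. The 6 later ones stay in the mITT set with zero change under the last-value rule.

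- mITT: 3 × 44/50 = 2.64
- All randomised: 3 × 44/55 = 2.40
- Ratio: 2.64/2.40 = 1.10

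The 10% excess is the same as for e = 5 above, but both estimates are below 3.

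**Step 3: no caffeine effect, early leavers 0.5 SD (2.5 units) worse.** If such patients are removed from caffeine and kept on placebo, the spurious difference is 2.5 × e/55: 0.14, 0.27 and 0.50 for e = 3, 6 and 11. Simulation with 60,000 runs per case and a two-sided t-test gives these type I errors:

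| removed from caffeine / placebo | type I error |
|---|---|
| 3 / 0 | about 5.1% |
| 6 / 0 | about 5.7% |
| 11 / 0 | about 7.6% |
| 6 / 3 | about 5.2% |

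Simulation error is about 0.1 percentage point. With equal, non-informative loss in both arms there is no bias under the null.

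**The case against.** A reader might infer that the rule strips caffeine-intolerant patients from the active arm, leaving an effect only in those who stayed on treatment. The text does not say that. The criterion is having no follow-up assessment, not intolerance. Someone who stops tablets in week 2 but attends month 1 stays in, and so does anyone who leaves later. Early placebo leavers are dropped as well. The entry criteria in 4.3.2 already remove known caffeine sensitivity and the cardiac conditions most likely to cause early trouble, so few people may be affected.

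A reader might also conclude that the trial is biased in favour of caffeine, or that its false-positive rate is clearly inflated. The protocol gives no early-loss rates by arm, so neither the direction nor the size is established. Type I error stays close to 5% unless nearly all planned dropout is early and confined to caffeine.

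Nor is it safe to say that the mITT analysis would report the full 3. That ignores later dropouts carried forward at baseline, as step 2 shows.

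The Fibroscan schedule is not fully settled either. The synopsis suggests a month-3 scan, and bloods are drawn at month 3. This weakens the argument about outcome data for people who reach month 3, but not for the month-1 threshold, where neither scan nor bloods are scheduled.

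These points limit the size and the wording of the concern. They do not remove the post-randomisation exclusion from the primary analysis. A separate analysis plan could add a sensitivity analysis, but the primary set is fixed in this document, and section 4.8 requires ethics committee approval for departures from it.

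**Conclusion.** The point holds in a limited form and should be corrected. Section 4.8 removes from the primary comparison any randomised participant without a follow-up assessment. The protocol's own account of the two products makes early loss that differs by arm foreseeable, and the threshold does not separate people with outcome data from those without.

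Under the stated assumptions, the estimate exceeds the all-randomised effect by 5.8% to 25% for 3 to 11 early caffeine leavers. The 25% case needs every planned caffeine dropout to leave in the first month. The effect on type I error is small except in that case, and it also requires excluded patients to have done worse. Confidence is medium, because no early-loss rates are given.

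**What to change.** In section 4.8:

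1. Define the primary set as all randomised participants in their assigned group, whether or not they attended a follow-up visit.
2. Replace both the mITT sentence and the last-value sentence with one missing-data rule for every participant without a month-6 value. Multiple imputation using arm, baseline value and the collected visit data is one option. Changing the mITT sentence alone would leave two conflicting rules in force.
3. Add placebo-based imputation as a sensitivity analysis. It is a debatable choice and need not be the primary method.
4. Keep the present mITT set as a sensitivity analysis, define what counts as a follow-up assessment, and report by arm how many are excluded and why.

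Separately, reconcile the synopsis with sections 4.6 and 5.5 and Table 2 on whether a month-3 Fibroscan is done.

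The cost is a rewritten paragraph and an imputation run. No extra patients, visits or tests are needed, because 55 per group already allows for 20% dropout. The downside is a possibly smaller estimate and a slightly wider interval than the mITT analysis would give.

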## 4.4. Sample Size Calculation and Statistics:

#### Sample size(n)

$$n = \sigma 2(Z\alpha/2 + Z\beta)2/delta$$

where,

- $Z\alpha/2=1.96$  (for  $\alpha = 0.05$ , two-tailed test)
- $Z\beta=0.84Z$  {\beta} = 0.84 $Z\beta=0.84$  (for 80% power)
- $\sigma=5 \cdot sigma = 5\sigma=5$  (Standard Deviation)
- $\Delta=3$ \Delta =  $3\Delta=3$  (Expected Mean Difference)

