## **6.3.** Fair participant selection

Fair participant selection will be ensured through objective inclusion criteria, avoiding unjustified exclusions. Randomization balanced key characteristics, minimizing bias.

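### The primary comparison of CAP and LSM leaves the test open between t-test and Mann-Whitney and does not use the baseline values already collected, which costs precision and leaves the target unfixed

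*Protocol*

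**What the plan says.** Protocol section 4.8 defines the primary comparison as follows: "Mean change in CAP score and LSM from baseline to 6 months will be compared between the 2 groups", and the test is to be made "using Independent T test or Mann Whitney U test depending on the distribution of data". It gives no criterion for judging the distribution, no default test and no covariate. It then adds that "Repeated measures ANOVA will be used for analysis of change in variables from baseline till end of study", without naming the variables or saying what role that analysis has. The threshold is stated as "P value less than 0.05 will be considered statistically significant".

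Section 5.5 schedules the scan twice: "Fibro scan will be done at the baseline and after 6 months at the completion of the study". Baseline CAP and LSM are therefore planned for every randomised participant.

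Section 4.4 bases the sample size on a difference in means ("two-tailed test", alpha 0.05, power 80%, mean difference 3). The value 5 is labelled only "Standard Deviation", with no endpoint or unit and no statement of whether it refers to a change or to a single measurement. After a 20% dropout allowance the result is 55 per group, 110 in total.

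**The concern.** The wording of 4.8 has two weaknesses.

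**The target is not fixed.** The t-test estimates a difference in mean change, which is the quantity 4.8 names and 4.4 plans for. Mann-Whitney tests for a shift in ranks and does not estimate that difference. With no rule for choosing, the observed data decide which question the primary analysis answers, and two analysts following the text could report different primary results.

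**Information already paid for goes unused.** A change score subtracts the whole baseline value, whatever its correlation with the week-24 value. ANCOVA estimates how much of the baseline to subtract. In a 1:1 trial it is asymptotically never less efficient, and it removes the effect of chance imbalance in the baseline of the outcome itself. The design aims at 80% power with nothing in reserve, so lost precision matters.

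**Working it through.** **Inputs.** From section 4.4: two-sided alpha 0.05, power 80%, difference 3, SD 5, dropout 20%. The correlation r between baseline and week 24 is not in the protocol; 0.3 to 0.9 is assumed below. SD 5 is read as the SD of change, also an assumption.

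**Step 1, the plan's own figure.** n per arm = 2 × 5² × (1.96 + 0.84)² / 3² = 43.6, so 44. With dropout, 44 / 0.80 = 55 per arm, 110 in total. The stated size reproduces. Power with 44 per arm is 80.4% by the normal approximation and 79.5% by the t distribution with 86 df. The t-based figures are used from here on.

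**Step 2, equal variances at both times.** With variance σ² at each time:

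- change score: 2σ²(1 − r)
- ANCOVA residual: σ²(1 − r²)
- ratio: (1 + r)/2

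The residual SD is 5 × √((1 + r)/2), and the equivalent number for the change-score test is 44 / ((1 + r)/2).

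| r | Variance ratio | Reduction | Residual SD | Power, 44 per arm | Equivalent n per arm |
|---|---|---|---|---|---|
| change score | 1 | – | 5.00 | 79.5% | 44 |
| 0.3 | 0.65 | 35% | 4.03 | 93.2% | 67.7 |
| 0.5 | 0.75 | 25% | 4.33 | 89.5% | 58.7 |
| 0.7 | 0.85 | 15% | 4.61 | 85.5% | 51.8 |
| 0.9 | 0.95 | 5% | 4.87 | 81.5% | 46.3 |

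**Step 3, CAP with the entry threshold.** Section 4.3.1 admits only CAP above 263. Suppose the values are bivariate normal with equal variances before selection, r is the correlation before selection, and selection acts on the analysed baseline. Let k be the share of baseline variance that remains. The residual variance is still σ²(1 − r²), and the change variance becomes σ²[(1 − r²) + (1 − r)²k]. The ratio is therefore (1 + r) / [(1 + r) + (1 − r)k]. The threshold's place in the distribution is not given. A cut 1 SD below the mean gives k = 0.63, and a cut at the mean gives k = 0.36.

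| r | Reduction, k = 0.63 | Power | Reduction, k = 0.36 | Power |
|---|---|---|---|---|
| 0.5 | 17% | 86% | 11% | 84% |
| 0.6 | 14% | 85% | 8% | 83% |
| 0.7 | 10% | 83% | 6% | 82% |

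For CAP the gain is thus about 6–17% of variance at r 0.5–0.7. LSM has no entry cut-off, so Step 2 fits it better.

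**Step 4, the choice of test.** This was simulated with 44 per arm and 10,000 runs per setting, under normal, skewed (lognormal) and heavy-tailed (t, 3 df) data. Under no effect, choosing by a Shapiro-Wilk pre-test (an assumed rule) kept type I error at 4.7–4.9%. Reporting whichever test was significant gave 5.7% (normal), 6.9% (skewed) and 6.5% (heavy-tailed). With an effect of 0.6 SD (3/5), the two tests disagreed on significance in about 5% of trials with normal data and 13% with heavy tails.

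**The case against.** The strongest reply is that the planned test is sound. Under randomisation the change-score t-test is unbiased and holds its level, and a disciplined choice by pre-test keeps type I error near 5%. This stands: the loss is in precision and in clarity of target, not in validity. It also stands that r is unknown, that at r = 0.9 the gain is about 2 points of power, and that truncation reduces it for CAP.

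A second reply is that covariates and normality criteria can be left to a statistical analysis plan, which may exist. That would answer a silent protocol. This one states an unadjusted, either/or primary test, so the text itself needs changing.

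A reader might infer more than the protocol supports:

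- **That the test is chosen after unblinding.** Section 4.8 does not say when or by whom the distribution is checked. Section 4.7 masks assignments until database lock, so a blinded, pooled check is compatible with the text.
- **That repeated-measures ANOVA is a second analysis of CAP and LSM.** Its variables are not named, and the sentence follows the one on secondary endpoints, several of which have three or more visits. If it were applied to two scan times, its group-by-time test would equal the change-score t-test and recover no precision.
- **That this ANOVA discards incomplete cases.** Section 4.8 uses the last available value for those lost to follow-up. Whether that is a good choice is a separate matter.
- **That section 6.3 shows an analysis fault.** "Randomization balanced key characteristics, minimizing bias" is a general statement on fairness. Balance holds in expectation, and chance imbalance does not invalidate the test.

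**Conclusion.** The point holds as a recommended improvement. The primary test should be a single one fixed in advance, and the collected baseline should be used.

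With SD 5 as the SD of change, 44 evaluable per arm, a difference of 3 and equal variances, power rises from about 79% to between 81% (r = 0.9) and 93% (r = 0.3). For CAP, with the entry threshold between 1 SD below the mean and the mean, it rises to about 82–87% at r 0.5–0.7. These figures rest on an assumed r and on an SD that 4.4 ties to no endpoint, so they show the scale of the gain and do not forecast it for CAP or LSM.

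The open choice of test adds at most about 2 points of type I error in the settings simulated, and only if it is misused. The more serious consequence is that the primary result may not estimate the mean difference the trial was sized for.

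**What to change.** Amend section 4.8 as follows:

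1. Name one primary model: ANCOVA of the week-24 value on treatment, with the baseline value of the same measure as the only covariate, reported as an adjusted mean difference with 95% CI. Do not leave optional covariates in this model.
2. Fix the scale for each endpoint before unblinding. For example, analyse CAP as measured, and LSM and FIB-4 (also a primary endpoint in section 2.4) on the log scale. State that the log-scale results are ratios.
3. Keep Mann-Whitney on the change as a sensitivity analysis only.
4. State which variables the repeated-measures ANOVA covers and that it is not the primary analysis of CAP or LSM.

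The cost is a few sentences. SPSS, the software named in 4.8, fits the model, and no extra scans, visits or participants are needed. The sample size can stay at 110, with the gain in precision held as a margin.
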